## 10.2.4 ADHERENCE AND RETENTION ANALYSES

Subjects lost to follow-up or terminated early for other reasons will be tabulated and summarized. For those subjects without a 3-month follow-up visit, the 3-month AzBio score will be imputed using last observation carried forward. That is, the 1 month Azbio score will be used as the 3 month AzBio score for the purposes of analysis. Only a small number of subjects are expected to be lost to follow-up, and benefit from the implant should be immediate, making this imputation method reasonable.

## 10.2.5 BASELINE DESCRIPTIVE STATISTICS

Baseline descriptive statistics will be summarized and reported for all subjects with available baseline data. All demographic and medical history information will be tabulated and presented as described in section 10.3.1 above.

## 10.2.6 ADDITIONAL SUB-GROUP ANALYSES

The change in AzBio sentence score and any change in aided bone conduction thresholds will be summarized by hearing loss type. No formal statistical comparison will be done between these two groups nor will any testing be formally done against the 10 percentage point increase as was done for the total combined group.

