## 2 INTRODUCTION

## 2.1 BACKGROUND INFORMATION

The MED-EL BONEBRIDGE Bone Conduction Implant is a transcutaneous, active bone conduction implant that was first implanted in 2011 in a European multicenter clinical trial. (Sprinzl, et al., 2013) Results from the initial clinical trial demonstrated effectiveness in restoring hearing and a low number of adverse events for subjects with mixed and conductive hearing loss. The BONEBRIDGE consists of an implantable part, the Bone Conduction Implant (BCI), and the external audio processor. The BCI consists of a magnet surrounded by the receiver coil, the electronics, a bendable transition, and the Bone Conduction-Floating Mass Transducer (BC-FMT).

A long history of experience with other available bone conduction implants, such as percutaneous BAHA devices, resulted in positive audiological outcomes but a high number of adverse events such as skin reactions, loss of osseointegration, and revision surgery. (Badran, Bunstone, Arya, Suryanarayanan, & Mackinnon, 2006) Development of the transcutaneous BONEBRIDGE system offers an intact skin solution that does not require osseo-integration and, thus, provides an active bone conduction implant with fewer post-operative complications.

In 2016, Schmerber et al. published on 13 adult patients with mixed or conductive hearing loss implanted with the BONEBRIDGE. (Schmerber, et al., 2016) No complications, device failures, or revision surgeries were reported in this patient group through 12 months post-implantation. Subjects demonstrated significant improvements in functional gain, speech perception in quiet, and speech perception in noise. These results were further confirmed by Weiss et al., who published data on 18 subjects implanted with BONEBRIDGE for mixed or conductive hearing loss. (Weiss, et al., 2016) No cases of infection or other complications were reported in this study. Riss et al. demonstrated similar results in subjects with mixed hearing loss and with atresia. (Riss, et al., 2014) On average, subjects with mixed hearing loss demonstrated 24.7 dB of functional gain, while subjects with atresia demonstrated 32.5 dB of functional gain. The authors hypothesized that the group with atresia demonstrated higher functional gain because they had a larger pre-operative air-bone gap.

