## 4 STUDY DESIGN AND ENDPOINTS

## 4.1 DESCRIPTION OF THE STUDY DESIGN

Approximately 30 subjects will be enrolled across three centers in this single-arm, repeated measures study, where each subject serves as his or her own control. Of the 30 subjects recruited into the study, 15 subjects with mixed hearing loss and 15 subjects with conductive hearing loss will be recruited across all three sites. After enrollment/baseline assessment confirms candidacy, qualified individuals will receive a BONEBRIDGE Bone Conduction Implant. Each subject will subsequently be fit with a SAMBA Audio Processor.

Activation will occur at two weeks post-implantation. Follow-up evaluations will occur at two weeks, one month, and three months post-activation. Soundfield thresholds, as well as speech perception testing in quiet and in noise, will be measured at the follow-up intervals. Results will be compared to the pre-operative unaided condition. In addition to any complications reported on a surgical questionnaire, safety outcomes will be collected and reported as the number and proportion of subjects experiencing a known risk. The three-month interval will be considered the primary safety and effectiveness endpoint.

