## 10 STATISTICAL CONSIDERATIONS

## 10.1 STATISTICAL HYPOTHESES

The primary endpoint is change in the AzBio sentence score from pre-operative levels to 3 months. An increase of 10 percentage points in this score is considered clinically relevant. The hypotheses to be tested are:

Ho: μΔ < 10 Ha: μΔ ≥ 10

where  $\mu\Delta$  is the mean change in the AzBio sentence scores from pre-operative to 3 months post-operative. These scores are represented as a percentage of words accurately repeated during testing.

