## 10.2 DESCRIPTION OF STATISTICAL METHODS

## 10.2.1 GENERAL APPROACH

Continuous variables will be summarized using mean, median, inter-quartile range, minimum, and maximum values. Categorical variables will be summarized using counts and percents. Testing of the primary endpoint will be done at the 0.025 level of significance.

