## 10.2.2 ANALYSIS OF THE PRIMARY ENDPOINTS

The mean change in AzBio sentence score from baseline to 3 months post-activation will be summarized as a continuous variable using the descriptive statistics described in section 10.4.1. Additionally, a one-sided, paired t-test comparing the mean change in AzBio sentence score to the superiority margin of 10 will be performed and the corresponding p-value will be reported. A p-value less than 0.025 will result in rejection of the null hypothesis indicating that the mean change in AzBio sentence score was greater than 10 percentage points.

The rate of occurrence of known risks will be summarized and reported as the number and proportion of subjects experiencing an event.

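### Recruitment is balanced by hearing-loss type, but the primary test ignores type and the by-type summary has no SD or interval: the test is conservative if the types differ, and a pass says nothing about either type alone

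*Combined protocol and SAP*

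**What the plan says.** Section 4.1 sets the recruitment mix: "15 subjects with mixed hearing loss and 15 subjects with conductive hearing loss will be recruited across all three sites". Section 5.3 softens this. It calls the split an intention, lets the total go above 30, and asks only for groups of about the same size.

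The hypothesis in section 10.1 has a single parameter, which "is the mean change in the AzBio sentence scores from pre-operative to 3 months post-operative". Section 10.2.2 plans "a one-sided, paired t-test comparing the mean change in AzBio sentence score to the superiority margin of 10", and section 10.2.1 sets the one-sided level at 0.025. Hearing-loss type appears in neither the estimate nor the standard error. The poolability check in section 10.4 looks at site only.

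Section 10.2.6 summarizes AzBio change by type and rules out more: "No formal statistical comparison will be done between these two groups nor will any testing be formally done against the 10 percentage point increase". It names no statistics, so the list in section 10.2.1 applies: "Continuous variables will be summarized using mean, median, inter-quartile range, minimum, and maximum values". That list has no SD, standard error or confidence interval.

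The background in section 2.1 gives a reason to expect that the groups might differ. It cites a study in which "subjects with mixed hearing loss demonstrated 24.7 dB of functional gain, while subjects with atresia demonstrated 32.5 dB of functional gain".

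**The concern.** A factor that shapes recruitment would normally appear in the analysis. Leaving it out here has two consequences.

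First, if the number of each type is held near 15, the difference between the type means adds nothing to the sampling error of the overall mean. The ordinary SD over all 30 changes still counts that difference as noise. The standard error is then too large, and the test gives away some of its 2.5%.

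Second, the objective speaks of adults with mixed or conductive loss, but the test concerns only the average of the two. That average can clear 10 while one type does not. The by-type table would show two means with no measure of precision, so a reader could not tell whether either type clears the margin.

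**Working it through.** **The plan's own figure.** Section 10.3 gives n = 30, mean change 30, SD 30 and alpha 0.025. The margin is 10. The noncentrality is (30 − 10)/(30/√30) = 20/5.477 = 3.65 with 29 df. The exact one-sided power is 94.16%, which matches the stated 94.2%.

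**Standard error.** Let D be the gap between the type means and s_w the within-type SD. Assume 15 subjects per type, equal SDs and normal changes.

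- True SE of the overall mean: s_w/√30.
- SE that the planned test expects to use: √[(s_w² + (30/29)(D/2)²)/30].
- To keep the plan's total SD at 30: s_w = √(900 − (D/2)²).

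Example, D = 20: s_w = √(900 − 100) = 28.28. The true SE is 28.28/5.477 = 5.16. The planned SE is √[(800 + 103.4)/30] = 5.49, so the ratio is 1.063.

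The documents give no AzBio difference between types, so D is an assumed range. Error rates and power below come from 400,000 simulated trials per row. The stratified test is the equal-weight mean of the type means with the pooled within-type SD and 28 df. Type I error is taken at an overall mean of 10, and power at an overall mean of 30.

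| D | s_w | True SE | Planned SE | Excess | Type I, planned | Type I, stratified | Power, planned | Power, stratified |
|---|---|---|---|---|---|---|---|---|
| 0 | 30.00 | 5.48 | 5.48 | 0% | 2.5% | 2.5% | 94.1% | 94.1% |
| 10 | 29.58 | 5.40 | 5.48 | 1.5% | 2.3% | 2.5% | 94.3% | 94.6% |
| 20 | 28.28 | 5.16 | 5.49 | 6% | 1.9% | 2.5% | 95.1% | 96.2% |
| 30 | 25.98 | 4.74 | 5.50 | 16% | 1.2% | 2.5% | 96.2% | 98.2% |
| 40 | 22.36 | 4.08 | 5.52 | 35% | 0.4% | 2.5% | 98.0% | 99.7% |

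If the plan's SD of 30 is read as the within-type SD, the excess at D = 10, 20, 30 and 40 is 1.4%, 5.6%, 12% and 21%. Planned power is then 93.9%, 92.8%, 90.8% and 87.5%, while stratified power stays near 94.2%.

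**A pooled pass with one type below 10.** With within-type SD 30, true gains of 52 and 8 pass the planned test in about 86% of trials, and gains of 40 and 5 in about 47%. At the planned overall mean of 30, one type falls below 10 only if D exceeds 40. At D = 40 the between-type part is (40/2)² = 400 of a total variance of 900, or 44%. If the overall mean is lower, a smaller gap is enough.

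**Precision by type.** At n = 15 and SD 30 the 95% half-width is 2.145 × 30/√15 = 16.6 points. A type with an observed mean of 20 would have an interval of about 3.4 to 36.6, and the observed mean must exceed about 26.6 before the lower limit passes 10. A formal test within one type at the planned effect would have 67% power, and both types would pass in about 45% of trials (0.67² = 0.45).

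**The case against.** There is a good case for leaving the plan alone.

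- **The split is a target.** If the mix were a random sample of the population, the pooled standard error would be right for that population's mean. This stands as a limit: the excess arises only as far as recruitment holds the counts near 15/15. Recruiting towards balance is not random sampling, though, so the limit does not remove the point.
- **The gaps are assumed.** The cited 24.7 and 32.5 dB are functional gain in mixed loss and atresia, and they do not convert to AzBio points. This stands. At a gap of 10 points the effect is negligible.
- **No test by type is a disclosed choice.** It agrees with a hypothesis about one overall mean, and n = 15 is too few for such tests. This stands, and no such test is proposed.
- **The by-type means would already reveal a weak type.** This is partly true: a mean of 5 would be visible, but its uncertainty would not.
- **The stratified test passes more often when one type is below 10.** With gains of 45 and 5 and within-type SD 28, the pass rate rises from 66% to 81%. The figures are right, but the hypothesis concerns the overall mean, which is 25 here, so rejection is correct. The by-type intervals serve the other question.

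A reader might infer that the primary test is invalid or leans towards a false success. The calculations show the reverse: the error is conservative.

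**Conclusion.** The point holds as a minor, inexpensive improvement. The primary test leaves out the factor on which recruitment is balanced. Its standard error is therefore overstated when the split is held near 15/15 and the types differ, by about 1.5% at a 10-point gap and 35% at a 40-point gap with total SD 30. Type I error stays at or below 2.5% throughout that range, so a positive result is not undermined.

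The more useful part concerns reporting. A pooled pass says nothing about each type, and the planned summary gives no interval to judge a type's mean against 10.

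A reader might also infer that the trial claims efficacy in each type, or that one type is likely to fall short. The documents support neither. Section 10.1 states one overall mean, and nothing in the plan gives AzBio gains by type.

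The sizes rest on assumed gaps, equal within-type SDs, normal changes (AzBio scores are bounded percentages, so this is an approximation) and a split of 15/15.

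**What to change.** 1. **Section 10.2.2.** Test the equal-weight mean of the two type means against 10, with SE = (s_w/2)√(1/n₁ + 1/n₂), where s_w is the pooled within-type SD. Use n₁ + n₂ − 2 df (28 at 15/15) and one-sided 0.025, and report the 95% CI. At 15/15 the estimate is the same as the planned mean.
2. **Section 10.2.6.** Report each type's mean change, SD and 95% CI beside the 10-point margin. Add no test and spend no alpha.
3. **Interpretation.** State that the primary result is an average over an equal mix of mixed and conductive loss, and that it does not establish the margin for each type.

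The cost is SAP wording, two table rows and one degree of freedom. If the types do not differ, power stays at about 94% (94.16% with 29 df, 94.11% with 28 df). The by-type intervals will be wide and may look less favourable than the pooled result. The change should be made before outcome data are examined.

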## 10.2.7 EXPLORATORY ANALYSES

Subjective improvement, as measured by the SSQ12 and HDSS questionnaires at three months post-activation, will be summarized. Responses will be compared to the pre-operative "everyday listening condition."

## 10.2.8 MULTIPLE COMPARISON/MULTIPLICITY

There is only one endpoint being formally tested in this study, therefore multiplicity is not an issue.

## 10.3 SAMPLE SIZE

A sample size of 30 subjects provides a power of 94.2% to detect a 10 percentage point increase in the AzBio sentence score from baseline to 3 months using an alpha level of 0.025. This assumes that an average increase of 30 percentage points with a standard deviation of 30. These initial estimates used for the sample size calculation came from the results for the Electric-Acoustic System (EAS) Investigational pivotal trial.

## 10.4 SITE POOLABILITY

Poolability of the data collected at the three centers will be established in the following manner. For each subject, the change from baseline to 3 months in the AzBio sentenc score will be

computed. The changes in AzBio sentence score will be analyized using a one-way analysis of variance in which site forms the levels of the single factor. The overall F-test will be used to demonstrate poolability of the primary endpoint data. If the p-value for the overall F-test is greater than or equal to 0.10 then the data will be considered poolable. If the p-value is less than 0.10, then additional methods (e.g. stratified analysis) may need to be employed in the analysis of the primary endpoint.

## 11 ETHICS/PROTECTION OF HUMAN SUBJECTS

## 11.1 ETHICAL STANDARD

The investigator will ensure that the study is conducted in accordance with regulations for the protection of human subjects found in 21 CFR Part 50 and 21 CFR Part 56.

## 11.2 INSTITUTIONAL REVIEW BOARD

The protocol, IC form, and any recruitment or participant materials will be submitted to the IRB for review and approval. IRB approval of both the protocol and IC must be obtained prior to beginning enrollment. Any amendment to the study protocol must also receive IRB approval before those changes are implemented in the study. Changes to the consent form will also be submitted to the IRB; at that time, a determination as to whether or not previously consented subjects need to be re-consented will be made.

## 11.3 INFORMED CONSENT PROCESS

## 11.3.1 CONSENT DOCUMENTS PROVIDED TO PARTICIPANTS

A consent form with detailed descriptions of the study device, study procedures, and risks will be given to the participant. Written documentation of IC is required prior to initiating any study-related activities. The IC template included with this protocol will be provided to each investigative site.

## 11.3.2 CONSENT PROCEDURES AND DOCUMENTATION

The IC process will be initiated prior to the participant's involvement in any study-related activities. Potential participants must be informed as to the purpose of the study and the potential risks and benefits known, or that can be reasonably predicted or expected. These risks are described in the written consent form.

Consent forms will be IRB approved, and the participant will be asked to read and review the document. The investigator will explain the research study to the participant and will answer any questions that may arise. All participants will receive a verbal explanation of the purpose, procedures, and potential risks of the study, as well as their rights as research participants.

The participant will sign the IC prior to being enrolled in the study. The investigator administering the IC will sign and date the form to indicate the document was sufficiently explained to the subject and their signature was witnessed. Consent may be withdrawn at any time during participation in the study. A copy of the signed IC will be provided to the subject, while the original will be retained by the investigator in the study file.

### 11.4 PARTICIPANT AND DATA CONFIDENTIALITY

The study protocol, documentation, data, and all other information generated will be kept in strict confidence. No information concerning the study or the data will be released to any unauthorized third party, without prior written approval of MED-EL. The investigator will guarantee that all persons involved will respect the confidentiality of any information concerning the study subjects.

All information provided to the investigator by MED-EL will be kept strictly confidential and confined to the personnel involved in conducting the study. Such personnel will be informed of the confidential nature of the information. It is recognized that this information may be communicated in confidence to the relevant IRB. In addition, no reports or information about the study or its progress will be provided to anyone not involved in the investigation, other than MED-EL or the relevant IRB, except if required by applicable law or regulation.

All data provided to MED-EL will be identified by a unique subject ID, thereby ensuring that the subject's identity remains unknown. The subjects should be informed in writing that their data will be stored and analyzed in a computer, with confidentiality maintained in accordance with applicable regulations.

The subjects should also be informed that authorized representatives of MED-EL and/or regulatory authorities may require access to parts of the site records (relevant to the study), including medical history, for data verification. The investigator is responsible for keeping a subject identification list of all subjects screened and enrolled.

## 12 DATA HANDLING AND RECORD KEEPING

## 12.1 DATA COLLECTION AND MANAGEMENT RESPONSIBILITIES

Prior to initiation of the study, investigators who may complete CRFs and are responsible for maintaining appropriate documentation will be identified. The investigator will be responsible for maintaining complete and accurate documentation of study procedures and medical records, including IC forms, for the duration of the study. Copies of correspondence with the IRB, Clinical Monitor, and MED-EL in general should also be maintained. Data on subjects will be collected in an anonymous manner, and any records sent to MED-EL should be de-identified.

The investigator is responsible for ensuring completeness, legibility, and accuracy of the recorded data. Source documentation should be completed in a neat, legible manner to ensure accurate interpretation of the data. When making changes or corrections, cross out the original

entry with a single line, and initial and date the change. Do not erase, write over, or use correction fluid or tape on the original document.

## 12.2 STUDY RECORDS RETENTION

Upon completion of the study, it is the investigator's responsibility to maintain all study records in a safe and secure location. Study-related documents should be kept for the duration of the study as required by 21 CFR Part 812.40 and the institution's IRB.

#### 12.3 PROTOCOL DEVIATIONS

Any noncompliance with the protocol or with GCP requirements will be reported to MED-EL in the protocol deviation log as a protocol deviation. Protocol deviations may be on the part of the investigator, participant, or other study staff. Corrective actions will be implemented based on the type and frequency of protocol deviations from each site. It is the responsibility of the investigator to be familiar with the protocol and to be vigilant regarding potential protocol deviations. Deviations should be submitted to MED-EL and the IRB in a timely manner, as required.

## 12.4 PUBLICATION AND DATA SHARING POLICY

All results generated in this study will be considered strictly confidential. No investigator may submit the results for publication without prior written permission of MED-EL. Once the study has concluded, publication of the multi-center data will be sought.

Authorship will be determined based on the amount of contribution to the study. The lead site (as designated prior to study initiation) may choose up to two authors for the multi-center publication. Additionally, the site with the most implanted subjects may also choose up to two authors. In the event that the lead site also enrolls the most subjects, then the site with the second largest number of subjects may choose up to three authors. The authors selected will be at the discretion of the principal investigator (PI) at each of the aforementioned sites. MED-EL reserves the right to include additional authors who have made substantial contributions to the study. Investigators may submit the results for presentation at conferences, with written approval from MED-EL.

The lead author will be the PI from the lead site. Last author will be at the discretion of MED-EL and could include the original PI from the lead site, if that person has since moved, or the PI at the site implanting the most subjects.

Any investigator wishing to present center-specific data at a national or international forum must inform MED-EL of the presentation title, forum, and date prior to submission of the abstract.

